# 7.1 Study Calendar

Required Studies	Pre-study 	1 cycle = 28 days		EOT 	LONG TERM FU 			
	Screening	C1D1 	C1D8	C1D15 	C1D22 	CnDn 		
Visit Windows (days) 	-28	+/-3	+/-3	+/- 3	+/-3	+/- 3	-28	+/-28
TREATMENT								
Olaparib		X	X	X	X	X		
Ascorbic acid 		X	X	X	X	X		
ELIGIBILITY								
Inclusion/exclusion review	X							
HRR status 	X							
Informed consent	X							
ECG	X							
PHYSICAL								
Medical and Cancer History	X							
Physical Exam, Weight and ECOG 	X	X	X	X	X	X	X	X
Vital Signs 	X	X	X	X	X	X	X	X
AE/Toxicity Notation 		X	X	X	X	X	X	X
Concurrent meds 	X	X	X	X	X	X	X	X
LABORATORY								
Chemistry 	X	X	X	X	X	$X^7$	X	X
Hematology 	X	X				$X^7$	X	X
Urinalysis	X							
INR and PT/APTT 	X							
Urine Creatinine 	X 	X 				X 	X 	
Testosterone	X							
PSA 	X	X				$X^7$	X	X
G6PD 	X							
CORRELATIVE								
Blood Samples 	NA	X 				X 	$X^{10}$	
Urine Samples 	NA	$X^{11}$				$X^{11}$	$X^{11}$	
Optional Biopsy (Encouraged)	X 	N/A				X 		
DISEASE ASSESSMENT								
Radiologic Evaluation/ RECIST 1.1  or PCWG2	X 					X 	X 	
LONG TERM FOLLOW-UP 								X 

- Longer delays to be approved by the study sponsor. IRB approval is required for all eligibility waivers prior to enrollment. The window for the baseline Radiologic Evaluation/RECIST 1.1 is 6 weeks prior to C1D1.
- Each treatment cycle is 4 weeks (28 days). Ascorbic Acid dosing must be 2 times per week except week 1 when Olaparib is giving alone. The first infusion must occur on day 1 of each cycle and the second infusion can occur any other day during the week as long as it is at least 24 hours from the prior infusion.
- Ports are recommended but not mandatory due to the frequency of infusion.
- 4 After screening, physical exams may be limited as indicated by symptoms. ECOG Eastern Cooperative Oncology Group performance status. Physical exam (including vital signs and weight), ECOG status, AE/Toxicity notation and concurrent medication review have a -3 day window of day 1 of the cycle.

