- Vital signs will be collected prior to infusion. Vital signs include temperature, blood pressure, respiration rate, and heart rate. Height is collected prestudy only. There is a -3 day window of day 1 of each cycle that the vital signs can be collected within.
- 6 Clinical Hematology: CBC with differential ANC, ALC, AEC, and platelet count; Serum Chemistry: sodium, potassium, chloride, bicarbonate, glucose, BUN, creatinine, ALT, AST, alkaline phosphatase, total bilirubin, total protein, albumin, calcium.
- Safety labs and PSA may be collected within a window of up to 3 days prior to scheduled visit/dosing. As of Cycle 2 and further cycles: at Day 1 visit, hematology and chemistry should be collected per hold parameters; at Days 8, 15, and 22 visits, only chemistry will be collected per hold parameters (hematology does not need to be drawn on Days 8, 15, and 22 unless clinically indicated). After C1D1, PSA is collected at CnD1 only (i.e., not weekly).
- 8 Urine creatinine will be collected at C1D1, C2D1 (4 weeks), C4D1 (12 weeks), and at EOT.
- G6PD testing: Red blood cell hemolysis may occur in people found to be deficient in the G6PD enzyme.
- Up to 50mL of whole blood will be collected for ctDNA analysis at each time point. Blood samples should be drawn at screening (or pre-dose C1D1), C2D1 post infusion (4 weeks), C4D1 (12 weeks) post infusion, and at EOT. Bloods do not need to be collected at C1D1 if they were collected within 7 days prior to the visit. γ H2AX will also be assessed at C1D1, C1D8, C2D1, C4D1 and progression.
- Urine samples of up to 15mL will be collected to assess F2-isoprostanes and 8-oxo-2'-deoxyguanosine at screening (or pre-dose C1D1), C2D1 (4 weeks), C4D1 (12 weeks), and at EOT. Urine samples do not need to be collected at C1D1 if they were collected within 5 days prior.
- 12 Research samples will be collected at the discretion of the PI based on availability of supplies and safety of patient and staff. An optional biopsy at baseline and at C4D1 (+/- 2 weeks) will be performed to look for γH2AX in tissue.
- CT scan (chest/abdomen/pelvis or MRI if patient has contrast allergy) and bone scan to be assessed at baseline and every 12 weeks (+/- 1 week), and at EOT (if clinically indicated by PI/Sub-I).

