- In order to minimize the need for research-only in-person visits, telemedicine visits may be substituted for in-person clinical trial visits or portions of clinical trial visits where determined to be appropriate and where determined by the investigator not to increase the participants risks. Prior to initiating telemedicine for study visits, the study team will explain to the participant what a telemedicine visit entails and confirm that the study participant is in agreement and able to proceed with this method. Telemedicine acknowledgement will be obtained in accordance with the Guidance for Use of Telemedicine in Research. In the event telemedicine is not deemed feasible, the study visit will proceed as an in-person visit. Telemedicine visits will be conducted using HIPAA compliant methods approved by the Health System and within licensing restrictions.
- There is a -7 day window to draw C1D1 labs.
- The EOT visit must occur within 28 days of the last dose of ascorbic acid or olaparib, whichever is later.

- Subjects who discontinued study treatment without documented disease progression should continue to be monitored for disease status by radiologic imaging. Disease monitoring should continue to be assessed every two months (+/- 2 weeks) until: 1) start of a new antineoplastic therapy (information of the new cancer therapy will be collected), 2) disease progression, 3) death, 4) withdrawal of consent, or 5) study closure, whichever occurs first. Survival status and subsequent therapies will be collected during long term follow-up (LTFU) every 6 months (+/- 4 weeks) from the date of last treatment, by phone or chart review, for 3 years or until study closure. Gather date of death, date of radiographic and/or PSA progression, start and stop dates for subsequent therapies.
-  INR and PT/APTT will be performed at baseline and at subsequent timepoints if clinically indicated.

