# 7.3.1 Clinical, Laboratory, and Radiographic Assessments

Every week, patients will have a non-fasting blood drawn for the values listed below. Repeat labs are not needed on C1D1 as long as visit is within 7 days of screening visit blood draw.

CMP

**Note:** Patients with creatinine clearance between 51-100 mL/min either at trial enrolment or during the course of the trial should be monitored every week for laboratory assessment and toxicity evaluation.

On Day 1 of each cycle, patients will have a non-fasting blood drawn for the values listed below. Repeat labs are not needed on C1D1 as long as visit is within 7 days of screening visit blood draw.

- CBC
- PSA

Every 3 cycles, patients will have radiographic studies:

- CT chest, abdomen, and pelvis with contrast
- NM bone scan

Laboratory Safety Assessments

Full hematology assessments for safety (hemoglobin, red blood cells [RBC], platelets, mean cell volume [MCV], mean cell hemoglobin concentration [MCHC], mean cell hemoglobin [MCH], white blood cells [WBC], absolute differential white cell count (neutrophils, lymphocytes, monocytes, eosinophils and basophils) and absolute neutrophil count or segmented neutrophil count and Band forms should be performed at each Day 1 visit and when clinically indicated. If absolute differentials not available, please provide % differentials. Coagulation [activated partial thromboplastin time (APTT) and international normalized ratio (INR)] will be performed at baseline and if clinically indicated. Patients taking warfarin may not participate in this study.

Biochemistry assessments for safety (sodium, potassium, calcium, glucose, creatinine, total bilirubin, gamma glutamyl transferase [GGT], alkaline phosphatase [ALP], aspartate transaminase [AST], alanine transaminase [ALT], urea or blood urea nitrogen [BUN], total protein, albumin) should be performed at each Day 1, Day 8, Day 15, and Day 22 visit.

Urinalysis by dipstick should be performed at baseline and at subsequent timepoints only if clinically indicated. Microscopic analysis must be performed by the hospital's local laboratory if required.

Bone marrow or blood cytogenetic samples may be collected from patients with prolonged hematological toxicities as defined under **Section 8.2.2.3** *Dose Modifications for Toxicities.* 

Additional analyses may be performed if clinically indicated.

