#### **7.4.2 EOT Visit**

Upon treatment discontinuation, patients will have an EOT Visit within 28 days of the last dose of ascorbic acid or olaparib, whichever is later. This visit will consist of the following:

- Conduct physical exam (including vital signs, weight)
- Perform laboratory tests: complete blood count w/diff, PSA, comprehensive metabolic panel
- Assess performance status (ECOG) (Appendix A)
- Review concurrent medications
- Assess AEs
- If patient is discontinuing participation in study, perform radiographic tests: CT C/A/P and NM bone scan (if these have not been performed in the prior 3 months)
- Blood and urine research samples

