# 7.5 Duration of Follow Up

Subjects will be followed for adverse events for a minimum of 30 days after the last dose of study drug or death, whichever occurs first. Subjects removed from study for unacceptable adverse event(s) will be followed until resolution or stabilization of the adverse event, initiation of new therapy for their cancer, or death, whichever occurs first.

Subjects who discontinued study treatment without documented disease progression should continue to be monitored for disease status by radiologic imaging. Disease monitoring should continue to be assessed every two months (+/- 2 weeks) until: 1) start of a new antineoplastic therapy (information of the new cancer therapy will be collected), 2) disease progression, 3) death, 4) withdrawal of consent, or 5) study closure, whichever occurs first.

Details of first and subsequent therapies for cancer and/or details of surgery for the treatment of cancer, after discontinuation of treatment, may be collected. Reasons for starting subsequent anti-cancer therapies including access to other PARP inhibitors or investigational drugs will be collected and included in the exploratory assessments of survival.

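### The study calendar and Section 7.4.2 give different rules for the end-of-treatment scan, which can decide between an rPFS event and censoring for men stopping on PSA, symptoms or a switch of therapy

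*Combined protocol and SAP*

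**What the plan says.** **EOT scan, calendar rule.** Section 7.1, footnote 13, schedules CT and bone scan at baseline and then "every 12 weeks (+/- 1 week), and at EOT (if clinically indicated by PI/Sub-I").

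**EOT scan, visit rule.** Section 7.4.2 says "If patient is discontinuing participation in study, perform radiographic tests: CT C/A/P and NM bone scan", on the condition "if these have not been performed in the prior 3 months". No clinical judgement is involved.

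**Timing.** Section 7.3.1: "Every 3 cycles, patients will have radiographic studies", which is 3 × 28 = 84 days. The calendar also says "The EOT visit must occur within 28 days of the last dose of ascorbic acid or olaparib, whichever is later", and "The window for the baseline Radiologic Evaluation/RECIST 1.1 is 6 weeks prior to C1D1".

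**Imaging after a stop.** Under Section 7.5, and the matching calendar footnote, men who stop without documented progression stay under imaging: "Disease monitoring should continue to be assessed every two months (+/- 2 weeks"). This ends at new antineoplastic therapy, progression, death, withdrawal or study closure.

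**What counts as progression.** Section 7.4.1 includes confirmed PSA doubling, symptomatic or clinical progression, and the physician's decision to start new systemic therapy, as well as imaging.

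**Endpoint.** In Sections 13.3 and 13.8, rPFS counts only radiographic progression or death. Other men are censored at their last progression-free assessment. Section 13.8 reports a 6-month Kaplan-Meier estimate with a 90% interval.

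**The concern.** Two pages of one protocol give different answers on whether a man leaving treatment has a closing scan. In a multi-center study, sites may follow different pages.

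The consequence depends on why he stops. A man who stops for toxicity goes into two-monthly imaging, so progression missed at EOT is normally picked up at a later scan. A man who stops on PSA doubling, symptoms or a decision to change therapy has, in the terms of 7.4.1, already progressed. Read literally, 7.5 then does not keep him under imaging, and where it does, imaging ends when the new therapy starts. For him the EOT scan is the last one the protocol schedules. Without it he is censored at an older scan, or at baseline if he stopped before week 12.

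Under the calendar rule, whether he is scanned also depends on how ill he appears, which ties detection of the endpoint to apparent prognosis.

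**Working it through.** **1. The plan's own figures.** The plan states no precision target for rPFS, so there is nothing to reproduce on this point. The PSA50 design does reproduce (12 men, 2 or more responses):
- alpha = 1 − 0.97^12 − 12(0.03)(0.97^11) = 0.0486
- power = 1 − 0.77^12 − 12(0.23)(0.77^11) = 0.801

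The EOT scan does not enter that calculation.

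**2. The rules disagree in both directions.** Take two men leaving the study.

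| Man at the EOT visit | Calendar | 7.4.2 |
|---|---|---|
| Baseline scan 14 weeks old, no clinical suspicion | no scan | scan |
| Last scan 10 weeks old, clinical suspicion | scan | not required |

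**3. How often the 3-month condition is met.** Let *s* be days into the 84-day interval at last dose (assumed uniform), *b* the days from baseline scan to C1D1 (0 to 42; zero after an on-study scan), and *g* the days from last dose to the EOT visit (0 to 28). Take 3 months as 91 days. The condition is s + b + g > 91.

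- After an on-study scan, g = 0: s cannot exceed 84, so 0%.
- After an on-study scan, g = 28: P(s > 63) = 21/84 = 25%.
- After an on-study scan, g uniform on 0–28: (21²/2)/28/84 = 9.4%.
- Before the first on-study scan, g uniform, b = 14: (7 + 14)/84 = 25%.
- The same with b = 28: (21 + 14)/84 = 42%.
- The same with b = 42: (35 + 14)/84 = 58%.
- Before the first on-study scan, b = 42 and g = 28: P(s > 21) = 63/84 = 75%.

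Taking 90 or 92 days moves these by about a point. The windows also allow 84 + 7 + 7 = 98 days between on-study scans and 42 + 91 = 133 days from baseline to the first one. With exponential stop times (step 4), the condition is met at 17–20% of non-radiographic stops overall, about 30% before the first on-study scan and 7–9% after it.

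**4. Effect on 6-month rPFS.** The documents give no event or stop rates, so these are assumptions: exponential radiographic progression (median 16 or 24 weeks), independent exponential non-radiographic stop (median 16, 30 or 52 weeks), scans every 12 weeks until the stop, EOT visit 2 weeks later, baseline scan 3 weeks before C1D1, no imaging after the stop. Kaplan-Meier rPFS at 26 weeks, 200,000 simulated men per row:

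| Medians (progression, stop) | 3-month rule | No EOT scan | Gap, points |
|---|---|---|---|
| 16, 16 | 0.320 | 0.355 | 3.5 |
| 16, 30 | 0.340 | 0.352 | 1.2 |
| 16, 52 | 0.349 | 0.353 | 0.4 |
| 24, 16 | 0.468 | 0.499 | 3.1 |
| 24, 30 | 0.492 | 0.499 | 0.7 |
| 24, 52 | 0.494 | 0.502 | 0.8 |

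No EOT scan is the extreme reading of the calendar rule, so these gaps are upper ends under these assumptions.

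**5. Two departures from those assumptions.**
- *Post-stop imaging for everyone.* With a scan every 8.7 weeks after every stop, the gap falls to 0.1–0.6 points.
- *Stopping that tracks progression.* If the stop hazard rises fourfold after radiographic progression (assumed; medians 16 and 16, EOT visit uniform over 0–28 days), no EOT scan reads 57% and the 3-month rule 43%. The true value is 0.5^(24/16) = 35% at the week-24 scan and 0.5^(26/16) = 32% at 26 weeks. A two-month look-back reads 34%.

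**6. One man in twelve.** Counting one stop as an event rather than censoring it takes the estimate from 1.00 to 11/12 = 0.917 with no earlier events, or from 0.75 to 0.75 × 8/9 = 0.667 after three: about 8 points either way.

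**The case against.** **The rules can be read together.** Section 7.4.2 is triggered by leaving the study, not merely stopping treatment. Men who leave get no later imaging and so must be scanned; men entering 7.5 follow-up can be scanned at discretion because imaging continues. This reading is sensible, but the protocol does not state it, and it does not settle the man whose stop already counts as progression under 7.4.1.

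**More scanning is not automatically less biased.** This is correct under independent stopping. With medians 16 and 16, a scan at every stop reads 28.1% against a true 32.4% at 26 weeks, a two-month look-back reads 29.5%, and the 3-month rule, at 32%, is closest. The ordering changes when stopping tracks progression, which is plausible for PSA and symptomatic stops. The case for a single rule is therefore consistent, suspicion-free ascertainment. It is not that any one look-back is unbiased.

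**Events can surface later.** Long-term follow-up (7.5.1) collects radiographic progression dates by phone or chart review. It schedules no scan to produce them, and the plan does not say whether they count in rPFS.

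**The effect is small beside the sampling error.** With 12 men, the 90% half-width is about 1.645 × √(p(1 − p)/12), or 21 to 24 points for p from 0.28 to 0.50. This stands, and it limits the severity.

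**Conclusion.** The two passages conflict and need reconciling. The effect is confined to rPFS, a secondary endpoint, and mainly to men stopping on PSA doubling, symptoms or a decision to start new therapy. In 6-month rPFS the written rules differ by about 0.4 to 3.5 points if stopping is independent of progression and no imaging follows, less if 7.5 imaging covers every stop, and more if stopping tracks progression. All these sizes rest on assumed event and stop times. Severity: minor.

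A reader might infer three stronger things that the documents do not support:

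- **That a 12-week schedule almost never meets the 3-month condition.** The 28-day EOT window and the 6-week baseline window make it roughly one stop in five. If it were almost never met, 7.4.2 would rarely require a scan and the conflict would be slighter.
- **That any stop may gain or lose an rPFS event depending on the page followed.** Men without documented progression stay under two-monthly imaging, so their event is usually dated later.
- **That the conflict is worth 2 to 7 points.** That range compares a scan at every stop with no scan at all, and neither passage requires a scan at every stop.

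**What to change.** - Replace the EOT wording in footnote 13 and in 7.4.2 with one objective rule, identical in both places and not dependent on investigator suspicion. It would apply to men stopping without radiographic progression whose last CT and bone scan is older than a fixed look-back. The two-month interval already in 7.5 is one option; the choice matters less than having a single rule.
- State whether that rule is triggered by stopping treatment or by leaving the study.
- State in 7.5, and in the matching calendar footnote, that imaging continues after a PSA-only or symptomatic stop until new therapy starts.

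The cost is a few lines of wording and an occasional extra standard scan in a trial of at most 15 men. For men already under two-monthly follow-up, it mostly brings the next scan forward. Sample size and the PSA50 analysis do not change.

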#### 7.2 Screening/Pretreatment Assessment (up to Day -28)

Before initiating any screening activities, the scope of the study should be explained to each patient. Patients should be advised of any known risks inherent to the planned procedures, any alternative treatment options, their right to withdraw from the study at any time for any reason, and their right to privacy. After this explanation, patients should be asked to sign and date a Notice of Privacy Practice research authorization/HIPAA form and an IRB-approved statement of informed consent that meets the requirements of the Code of Federal Regulations (Federal Register Vol. 46, No. 17, January 27, 1981, part 50).

The following assessments will be performed at the screening visit:

- Obtain informed consent and research authorization.
- Record demographics (including age) and medical history (including prior treatment for prostate carcinoma).
- Conduct physical exam (including vital signs, height/weight).
- Obtain history regarding prior treatment history for prostate cancer (including history of ADT, and history of radiation therapy or other local therapy).
- Obtain histologic/radiographic confirmation of disease. If radiographic studies have not been performed within 6 weeks prior to Cycle 1 Day 1, they must be obtained as part of screening.
- Perform laboratory tests: complete blood count w/diff, PSA, comprehensive metabolic panel, urinalysis, G6PD, testosterone.
- Baseline ECG
- Confirmation of 25% PSA rise on prior therapy.
- Determine suitability for olaparib and ascorbate therapy.
- Discuss concurrent medications.

Relevant information should be documented for registration and monitoring purposes. The institutional registration should be finalized, and appropriate documents faxed or emailed to the lead site/sponsor per **Section 6.0**.

Information for patients who do not meet the eligibility criteria to participate in this study (i.e. screening failures) should be captured in consortium database at the pretreatment assessment.

For any subject that has a DNA repair gene mutation identified during screening and is therefore not eligible for this trial will be referred to medical genetics for counseling and consideration of further targeted testing to determine if the identified mutation is present in the germline.

# 7.3 Treatment/Intervention Period

Patients will be seen on D1 of each cycle of study therapy (consisting of 28 days  $\pm$ 3 days). The following assessments will be performed at each visit:

- Conduct physical exam (including vital signs, weight)
- Obtain and medical history changes from prior assessment
- Assess performance status (ECOG). (Appendix A)
- Review concurrent medications

# 7.3.1 Clinical, Laboratory, and Radiographic Assessments

Every week, patients will have a non-fasting blood drawn for the values listed below. Repeat labs are not needed on C1D1 as long as visit is within 7 days of screening visit blood draw.

CMP

**Note:** Patients with creatinine clearance between 51-100 mL/min either at trial enrolment or during the course of the trial should be monitored every week for laboratory assessment and toxicity evaluation.

On Day 1 of each cycle, patients will have a non-fasting blood drawn for the values listed below. Repeat labs are not needed on C1D1 as long as visit is within 7 days of screening visit blood draw.

- CBC
- PSA

Every 3 cycles, patients will have radiographic studies:

- CT chest, abdomen, and pelvis with contrast
- NM bone scan

Laboratory Safety Assessments

Full hematology assessments for safety (hemoglobin, red blood cells [RBC], platelets, mean cell volume [MCV], mean cell hemoglobin concentration [MCHC], mean cell hemoglobin [MCH], white blood cells [WBC], absolute differential white cell count (neutrophils, lymphocytes, monocytes, eosinophils and basophils) and absolute neutrophil count or segmented neutrophil count and Band forms should be performed at each Day 1 visit and when clinically indicated. If absolute differentials not available, please provide % differentials. Coagulation [activated partial thromboplastin time (APTT) and international normalized ratio (INR)] will be performed at baseline and if clinically indicated. Patients taking warfarin may not participate in this study.

Biochemistry assessments for safety (sodium, potassium, calcium, glucose, creatinine, total bilirubin, gamma glutamyl transferase [GGT], alkaline phosphatase [ALP], aspartate transaminase [AST], alanine transaminase [ALT], urea or blood urea nitrogen [BUN], total protein, albumin) should be performed at each Day 1, Day 8, Day 15, and Day 22 visit.

Urinalysis by dipstick should be performed at baseline and at subsequent timepoints only if clinically indicated. Microscopic analysis must be performed by the hospital's local laboratory if required.

Bone marrow or blood cytogenetic samples may be collected from patients with prolonged hematological toxicities as defined under **Section 8.2.2.3** *Dose Modifications for Toxicities.* 

Additional analyses may be performed if clinically indicated.

Any clinically significant abnormal laboratory values should be repeated as clinically indicated and recorded on the eCRF.

In case a subject shows an AST **or** ALT ≥3xULN **or** total bilirubin ≥2xULN please refer to **Appendix D** 'Actions required in cases of combined increase of Aminotransferase and Total Bilirubin – Hy's Law', for further instructions.

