# 8.0 DOSING DELAYS/MODIFICATIONS

# 8.1 Dosing Delays

All scheduled cycles occur over a 28-day period. If necessary, treatment may be delayed for up to 4 weeks. If treatment is delayed more than two weeks, the Principal Investigator must be contacted for further instructions on continued treatment. Additional delays or modifications to the treatment schedule must be approved by the Protocol Chair. When the delay is due to toxicity, then the next cycle may begin with a dose reduction.

Ascorbic acid will be withheld for the following drug-related toxicities:

- $Cr \ge 1.6 \times ULN$  (for patients with  $Cr \ge 1.6 \times ULN$ , calculated or measured creatinine clearance must be  $\ge 50 \text{ mL/minute}$  (Cockcroft-Gault))
- Common Terminology Criteria for Adverse Events (CTCAE) Grade 3 or 4 non-hematologic toxicity excluding asymptomatic electrolyte aberrations
- Any AE, laboratory abnormality, or intercurrent illness that, in the judgement of the investigator, warrants delaying the dose of study medication

Olaparib will be withheld for the following drug-related toxicities:

Absolute neutrophil count
 Platelets
 Hemoglobin
 Total bilirubin
 AST (SGOT)/ALT(SGPT)
 ≤ 750/ mm³, see Table 8
 ≤ 8 hgb, If < 10, see Table 7

 ≥ 1.5XULN
 ≥ 2.5 x ULN (<5x ULN if with known liver m

• AST (SGOT)/ALT(SGPT)  $\geq 2.5 \text{ x ULN (<}5\text{x ULN if with known liver metastases}$  provided bilirubin is normal)

- Common Terminology Criteria for Adverse Events (CTCAE) Grade 3 or 4 non-hematologic toxicity excluding asymptomatic electrolyte aberrations
- Any AE, laboratory abnormality, or intercurrent illness that, in the judgement of the investigator, warrants delaying the dose of study medication

If dosing parameters for Ascorbic Acid are not met, study participants may continue with olaparib therapy. If dosing parameters for olaparib or are not met, study participants may continue with Ascorbic Acid therapy. Dose interruptions are allowed as required, for a maximum of 4 weeks. Patients who require an interruption in olaparib or ascorbic acid for >4 weeks due to toxicity must permanently discontinue study drug unless an exemption is granted by the protocol chair (Refer to section 13.6 for stopping rule). Where toxicity reoccurs following re-challenge with study treatment, then the patient should be considered for dose reduction or must permanently discontinue study treatment per investigator judgement.

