# 13.2 Primary Endpoint Definition

The primary endpoint in this study is based on  $PSA_{50}$  response.  $PSA_{50}$  response will be defined as a decrease in the PSA to 50% less than the baseline PSA upon enrollment in the trial. The decrease must be confirmed by a second measurement at least 4 weeks apart. PSA values will be measured monthly during the trial.

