## 13.8 Analysis of Secondary Endpoints

The **safety analysis** will be performed in all subjects receiving combination olaparib and IV ascorbic acid. AE data will be listed individually and incidence of AEs summarized by system organ class and preferred terms within a system organ class for each treatment group. When calculating the incidence of AEs, each AE (based on preferred terminology defined by Medical Dictionary for Regulatory Activities (MedDRA; Version 13.1, or later) will be counted only once for a given subject. In analyses of grade and causality, if the same AE occurs on multiple occasions, the highest grade and strongest relationship to study drug will be assumed. If 2 or more AEs are reported as a unit, the individual terms will be reported as separate experiences. Changes in vital signs, hematology and clinical chemistry parameters from baseline to the end of the study will be examined. Toxicity will be tabulated by type and grade. Toxicities will be characterized according to the CTCAE version 5.0 Treatment-emergent changes from normal to abnormal values in key laboratory parameters will be identified.

Radiographic progression-free survival (**rPFS**) is defined as the number of months from initiation of therapy (cycle 1, day 1) to date of first radiographic progression, death from any cause, or last patient evaluation. Patients must receive at least one dose of olaparib and IV ascorbic acid to be considered evaluable. Radiographic progression will be determined by modified RECIST criteria 1.1 by development of two or more new bone lesions not consistent with tumor flair for prostate cancer working group 2. Patients who have not progressed or died will be censored at the last date they were assessed and deemed progression-free. rPFS will be summarized and six month estimates for rPFS will be reported using the Kaplan-Meier method with 90% confidence intervals.

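### Imaging is timed by cycles in Section 7.3.1 and by calendar weeks in Section 7.1; if sites follow the cycle rule, dose delays can push the second scan past the six-month rPFS landmark

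*Combined protocol and SAP*

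**What the plan says.** Imaging has two on-treatment rules. Section 7.3.1: "Every 3 cycles, patients will have radiographic studies". Section 7.1, imaging footnote: CT and "bone scan to be assessed at baseline and every 12 weeks (+/- 1 week), and at EOT". The same calendar fixes the nominal cycle: "Each treatment cycle is 4 weeks (28 days" days).

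Section 8.1 provides for late cycles: "If necessary, treatment may be delayed for up to 4 weeks". It adds that, after a toxicity delay, the next cycle may start at a reduced dose, so the plan foresees delayed cycle starts. It also lets one drug continue while the other is held.

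PSA also has two descriptions. The laboratory footnote in Section 7.1: "After C1D1, PSA is collected at CnD1 only (i.e., not weekly"). Section 7.3.1 likewise puts PSA on Day 1 of each cycle. Section 13.2: "PSA values will be measured monthly during the trial".

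For the analysis, Section 13.8 states that "six month estimates for rPFS will be reported using the Kaplan-Meier method", with 90% confidence intervals. The rPFS events are radiographic progression and death (Sections 13.3 and 13.8).

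**The concern.** A cycle rule and a calendar rule coincide only while treatment runs to time. Once a cycle start slips, the two sections give different scan dates, and no section says which prevails or that scans hold their place during a delay.

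Under the cycle rule, assessment timing depends on toxicity: a man with longer delays is scanned later. Progression is dated at the scan that shows it, so a man who progressed between scans is counted as progression-free for longer. The second scan is due only about two weeks before the six-month landmark, so a modest slip is enough to put it on the wrong side. There is no control arm to share or offset the effect.

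The PSA schedule raises a parallel but separate question for the two PSA time-to-event endpoints.

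**Working it through.** **The plan's own figure.** The documents give no design figure for rPFS. The only one is the PSA50 rule in Section 13.5: 12 patients, 2 or more responses, 3% against 23%. It reproduces exactly:
- alpha = 1 − 0.97^12 − 12(0.03)(0.97^11) = 0.0486
- power = 1 − 0.77^12 − 12(0.23)(0.77^11) = 0.801

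Nothing below touches it.

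**Scan dates.** Three cycles are 3 × 28 = 84 days (week 12) and six are 168 days (week 24), so the rules agree without delay. Six months is 365.25/2 = 182.6 days (26.1 weeks). The margin is 182.6 − 168 = 14.6 days.

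| Cumulative slip | Second scan, cycle rule | Within six months? |
|---|---|---|
| 0 days | week 24 | yes |
| 14 days | week 26 | yes |
| 15 days | week 26.1 (day 183) | no |
| 28 days | week 28 | no |

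Under the calendar rule the second scan falls on day 161-175, always before the landmark.

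**Effect on six-month rPFS (assumptions, not document figures).** Take exponential time to radiographic progression with median m weeks, S(t) = 0.5^(t/m). Progression is seen only at scans; deaths and dropout are ignored. Apparent six-month rPFS is then S at the last scan on or before week 26.1.

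For m = 16:
- Underlying value: S(26.1) = 32.3%.
- Calendar clock: S(24) = 35.4%.
- One man with a 4-week slip on the cycle clock: S(16) = 50.0% if the slip comes before scan 1, S(12) = 59.5% if after it.

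For a cohort, let the total delay d be uniform over a range, with half the delays before scan 1. A delayed man contributes S(24 + d) if 24 + d ≤ 26.1. Otherwise he contributes S(12 + d) for an early delay or S(12) for a late one. If a fraction f is delayed, the estimate is (1 − f) × 35.4% + f × (average for delayed men).

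| Delay range | Average, delayed men | f = 20% | f = 40% |
|---|---|---|---|
| 2-4 weeks | 54.8% | 39.2% | 43.1% |
| 0-4 weeks | 44.3% | 37% | 39% |
| 0-2 weeks | 33.9% | 35.1% | 34.8% |

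Example: 0.8 × 35.4 + 0.2 × 54.8 = 39.3, or 39.2 with unrounded inputs.

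In the 0-2 week row no second scan crosses the landmark. It simply occurs a little later and sees slightly more progression, so the estimate dips marginally.

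In the 2-4 week, 40% case, placing all delays early or all late gives 41.7% to 44.5%. With m = 24, the calendar reading of 50% (underlying 47.1%) becomes 53-57% for delays of 2-4 weeks.

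**PSA.** Draws tied to cycle Day 1 are 4 weeks apart without delay. One 4-week delay makes the gap 4 + 4 = 8 weeks, against the monthly interval in Section 13.2.

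**The case against.** The best defence is that Section 7.1 already contains the right rule. A site that follows the imaging footnote keeps every scan within a week of its calendar date, and there is no inflation. This stands: a reader might infer that the plan as written inflates six-month rPFS, but the documents support only that it can do so where 7.3.1 is followed.

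The route to a long slip is also narrower than the 4-week allowance suggests. One drug may continue while the other is held, so many toxicity holds need not move Day 1. Section 8.1 requires contact with the Principal Investigator beyond two weeks and approval of additional delays. Other text uses 2-week limits (Section 7.4 and Tables 7 and 8), while Section 8.1 and the non-hematological guidance in 8.2.2.3 allow 4. A slip of 15 days or more is therefore possible, but how often it would occur is unknown.

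The size depends on the assumed delay range, as the table shows. Nor should the 35% be read as the true rate: it is what a week-24 scan reports of an underlying 32%, and the calendar rule keeps that gap of about 3 points.

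A reader might also link PSA timing to rPFS. The definitions rule this out, because PSA is not an rPFS event. The PSA footnote may be meant mainly to exclude weekly draws, and a 28-day interval is monthly in ordinary usage, so the PSA mismatch too appears only after a delay.

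Finally, rPFS is secondary and carries no test or threshold. With 12 men, a rough 90% interval around 35% is ±1.645 × √(0.35 × 0.65/12) = ±23 points, wider than any shift shown. That limits the priority. It does not remove the contradiction, because the error beyond two weeks of slip is systematic and related to toxicity.

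**Conclusion.** The point holds in a conditional form. Sections 7.3.1 and 7.1 give different scan dates once a cycle start slips, and no passage settles which governs. Six-month rPFS is materially inflated only if sites follow 7.3.1 and a man's cumulative slip exceeds about 2 weeks.

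Under the assumed 16-week median with 20-40% of men delayed, the upward shift from the calendar reading is about 4-8 points for delays of 2-4 weeks, about 2-4 points for 0-4 weeks, and essentially nil for 0-2 weeks. Both the median and the delay pattern are assumptions.

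The PSA mismatch is separate: after a 4-week delay it can postpone event dates for PSA PFS and time to PSA doubling. Its size has not been estimated. The PSA50 sample size and decision rule stand. This should be corrected, but it is a harmonisation of wording rather than a flaw in the design.

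**What to change.** - **Imaging.** In Section 7.3.1, replace the three-cycle interval with every 12 weeks (+/- 1 week) from C1D1, not shifted by dose delays. This matches the Section 7.1 footnote.
- **PSA.** In Section 7.3.1 and the laboratory footnote of Section 7.1, state PSA every 4 weeks from C1D1 regardless of dose delays, consistent with Section 13.2. The exclusion of weekly draws can stay.
- **Off treatment.** Leave the two-monthly imaging in Section 7.5 unchanged. Putting it on the 12-week grid would make those scans less frequent, a loss that this point does not justify.

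The cost is an occasional scan or PSA draw outside a cycle Day 1 visit. No dose, treatment rule or sample size changes.
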